## STATEMENT OF COMPLIANCE

The trial will be conducted in accordance with good clinical practice, applicable United States (US) Code of Federal Regulations (CFR), and the NIDILRR Terms and Conditions of Award. The Principal Investigator will assure that no deviation from, or changes to the protocol will take place without prior agreement from the Investigational New Drug (IND) sponsor, funding agency and documented approval from the Institutional Review Board (IRB), except where necessary to eliminate an immediate hazard(s) to the trial participants. All personnel involved in the conduct of this study have completed human subjects training.

The protocol, informed consent form(s), recruitment materials, and all participant materials will be submitted to the IRB for review and approval. Approval of both the protocol and the consent form must be obtained before any participant is enrolled. Any amendment to the protocol will require review and approval by the IRB before the changes are implemented to the study. All changes to the consent form will be IRB approved; a determination will be made regarding whether a new consent needs to be obtained from participants who provided consent, using a previously approved consent form.

## 1 PROTOCOL SUMMARY

### 1.1 SYNOPSIS

Title:	The Effect of Gentamicin Intravesical Instillations on Decreasing Urinary Tract Infections in Patients with Neurogenic Bladder after SCI: A Clinical Trial
Study Description:	A trial to assess the efficacy of intravesical gentamicin on the occurrence rate of urinary tract infections (UTIs) and bladder complications in patients after SCI, and to assess its effectiveness in promoting overall QOL, community living, and participation.
Objectives:	
Primary Objective: Evaluate efficacy of intravesical gentamicin in reducing the number of urinary tract infections during a six-month period.
 
Secondary Objectives: Examine the effectiveness of gentamicin in decreasing associated bladder and bowel complications.
 
Tertiary Objective: Examine the effect of gentamicin on improving health-related quality of life and community participation.

Endpoints:	
Primary Endpoint: Number of UTIs
 
Secondary Endpoints: Number of complications
 
Tertiary Endpoints: Quality of life and participation scores

Study Population:	Adults with a traumatic or non-traumatic SCI with neurogenic bladder and recurrent urinary tract infections
Phase:	Phase 2/3
Description of Sites/Facilities Enrolling Participants:	Michigan Medicine (academic medical institution in southeastern Michigan affiliated with the University of Michigan)
Participants:	Department of Physical Medicine and Rehabilitation Department of Urology
Description of Study Intervention:	Intravesical gentamicin + saline instillations
Study Duration:	12 months
Intervention Duration:	6 months

 Throughout this document, six months refers to 180 days.

## 1.2 SCHEMA

[figure not shown]

Figure 1. Study Flowchart; refer to Schedule of Activities (Table 1) for study procedures by visit

### 1.3 SCHEDULE OF ACTIVITIES (SOA)

Procedures	Screening	Visit 1 (Baseline) 	Visit 2	Visit 3 (Follow-Up Interview)	Optional Post-Intervention Survey
	Day -30 to 0	D0	Day 180±30	Day 90 - 30 / + 90 post-intervention	Day 90 - 30/+365 post-intervention
Medical Record Review	X	X	X	X	
Informed consent		X			
Demographics	X				
Clinical History	X	X	X	X	
Current Medications	X	X	X	X	
Urine Analysis (UA; plus culture if needed) 	X		X		
Pregnancy test	X				
Complete Blood Count		X	X		
Comprehensive Metabolic Panel		X	X		
Self-report measures of QOL 		X	X		
Safety Review 			X		
Every 30 days +/- 2 business days: ship study product		↔			
Schedule bi-weekly phone calls 		↔			
Satisfaction survey 					X

 Participation will commence once eligibility is confirmed via urine analysis (or culture for those individuals with a positive UA); an order for study product will be faxed/mailed to the Research Pharmacy; intervention start date will be the first dose listed on the dosing diary. If the dosing diary is not available, the intervention start date will be recorded as the date told to the study team by the participant and documented in the REDCap database.

 A rapid UA will be performed as part of standard of care at the time of screening; UAs at Visit 2 will be study-paid; positive tests will be followed with a urine culture; test results usually take about 4 days

 QOL measures include the following standardized surveys: Neurogenic Bladder Symptom Score; Neurogenic Bowel Dysfunction Score; SF-Qualiveen; SCI-QOL Measurement System's *Bladder Management Difficulties*, *Bladder Complications*, *Bowel Management Difficulties*, and *Satisfaction with Social Roles and Activities*; and Community Participation Indicators Scale (see Section 8.1, "Efficacy Assessments")

 Study team will make phone calls every two weeks +/- 3 business days to participants throughout the study period to ask about UTIs, adverse events, compliance and general health updates.

 Study team will conduct this visit, likely over the phone, within 30 days after the participant's final instillation in order to assess any adverse events or reactions while the study drug is washing out of the participant's system

 Study team will contact participants at least 60 days post-intervention for an optional survey to assess their perception of Gentamicin use, challenges and satisfaction with study participation. Participants may be contacted up to 1 year after the end of their participation.

## 2 INTRODUCTION

### 2.1 STUDY RATIONALE

This proposal addresses a critical health issue affecting those living with spinal cord injury (SCI), that of recurrent urinary tract infections (UTIs) and their effects on health, quality of life (QOL), community living and participation. While mortality due to urinary tract complications has decreased during the last several decades in persons with SCI, UTIs remain one of the eight leading causes of death among SCI patients, and their effects on QOL and one's ability to function in the community are clearly documented in the literature. Although antibiotics have been used to treat UTIs, for those with recurrent infections, oral antibiotic treatment is not always effective and can lead to infections that are resistant to treatment. Intravesical (occurring within the bladder) instillation of a gentamicin solution (a generic antibiotic often used to treat UTIs) has been used clinically in adults with SCI for over 20 years. The process is quite simple and requires flushing the bladder with the solution. Yet, the effectiveness of intravesical gentamicin in prevention of UTIs has not undergone rigorous efficacy testing in SCI. **This study proposes a clinical trial of intravesical gentamicin to reduce the incidence of UTIs in persons with SCI and to assess its effectiveness in promoting overall QOL, community living and participation.**

Two important reasons guided our decision to study the effects of prevention of UTIs with gentamicin on QOL. First, our discussions with colleagues and collaborators show that most SCI patients who use gentamicin for prevention of UTIs are very satisfied with results. Second, there is a lack of clear evidence in the field for broad outcome measures, shown by the limited use of QOL and community participation measures in clinical trials.

Due to its potential efficacy, a robust trial of intravesical gentamicin in person with SCI having recurrent infections is needed. The selection of gentamicin for this Clinical Trial (CT) has several reasons: 1) its ongoing use by patients with SCI and recurrent infections; 2) its potential efficacy as an antimicrobial treatment that shows good results in persons with neurogenic bladder; and 3) its apparent drug safety in this route of administration, with no expected systemic side effects per previous studies.

### 2.2 BACKGROUND

This study addresses a critical health issue for those living with SCI, that of recurrent UTIs and their effects on health, QOL, community living and participation. While mortality due to urinary tract complications has decreased during the last several decades in persons with SCI, UTIs remain one of the eight leading causes of death among SCI patients, and their effects on QOL and one's ability to function in the community are clearly documented in the literature. Although antibiotics have been used to treat UTIs, for those with recurrent infections, oral antibiotic treatment is not always effective and can lead to infections that are resistant to treatment. Intravesical (occurring within the bladder) instillation of a gentamicin solution (a generic antibiotic often used to treat UTIs) has been used clinically in adults with SCI for over 20 years.

Inappropriate bladder management can cause complications including recurrent UTIs, sepsis, and kidney damage due to chronic urinary retention. The instillation process is quite simple and requires flushing the bladder with the solution. However, the effectiveness of intravesical gentamicin in prevention of UTIs has not undergone rigorous efficacy testing in SCI. This study will also contribute new knowledge by examining the associations between neurogenic bladder and bowel complications. It will also examine the impact of this treatment on QOL and community participation among persons with SCI.

Risk factors for UTIs include requiring catheterization by a caregiver, build-up of urinary calculi in the bladder, incomplete voiding, elevated intravesical pressure and catheter use. There exists little consensus on treatment of UTIs in this population. While literature suggests the superiority of clean intermittent catheterization (CIC) for those who are able to perform it, a 2012 systematic review suggested that no universal recommendations could be made. The dose of gentamicin was selected based on similar protocols available in the literature.

## 2.3 RISK/BENEFIT ASSESSMENT

### 2.3.1 KNOWN POTENTIAL RISKS

The overall risk of intravesical gentamicin for the management of recurrent UTIs in patients with neurogenic bladder is low. The method of daily bladder instillations is a common clinical strategy at Michigan Medicine, Department of Urology for specific patients (i.e. those with neurogenic bladder and frequent symptomatic UTIs), and it is one that is generally well-received by both patients and care givers. A retrospective analysis of Michigan Medicine patients showed mild and rare adverse events while using Gentamicin bladder instillations. Likewise, Abrams et al. and Defoor et al. suggest that gentamicin as prophylaxis against recurrent UTIs is well-tolerated and of minimal risk.

*Urinary tract infection (primary outcome)* – Recurrent UTIs are a likely occurrence in this study population. Participants will be instructed to contact their physicians at U-M who provide urological care in the event of UTI symptoms and can expect to be managed according to standard clinical practice (e.g. a course of oral antibiotics). The study team will query participants bi-weekly for any UTI occurrences (including symptoms and treated cases) and prompt the participant to follow-up accordingly if they have not already done so.

*Risks associated with regular bladder catheterization* – There is *potential for trauma at the site of insertion* of the catheter. The risk associated with participation in this study is no greater than experienced by these patients as part of their typical catheterization process. Likewise, there is *a risk of contamination from using non-sterilized equipment*. Again, this risk is commensurate with participant's risk exposure during their typical catheterization process. Participants and/or their caregivers will typically be experienced in the proper and safe manner of clean intermittent catheterization, but all will receive education and guidance in proper and hygienic catheterization practices with their study materials.

*Burden* - Cox et al describe daily gentamicin instillations as "minimally burdensome" as it only adds one additional step to the patient's normal nightly catheterization routine. The expected additional time is 1-3 minutes. This burden may be experienced by both the patient and a caregiver. Participants will be told that if the additional burden is too great they may withdraw from the study without repercussion to them or their normal clinical care.

*Bladder spasms* – Waites et al reported a small percentage (<5%) of patients with bladder spasms related to bladder irrigation using compounds other than gentamicin. It is unclear whether these experiences were related to the process itself or to the product. There were no reports of bladder spasms in the Cox analysis. To minimize the likelihood that the instillation process contributes to bladder spasms, we will provide standard patient and caregiver education on how to perform the instillation and on usual patient experiences. Participants will be told that withdrawal without repercussion is an option in the event the study proves more onerous than anticipated or desired.

*Allergic reaction or sensitivity to study product* – Individuals allergic to gentamicin or any component of the study product may experience allergic-type reactions including mild asthmatic episodes to anaphylaxis. The overall prevalence of reactive sensitivities is likely to be low (per product insert and clinical experience of [name] [name], Associate Professor, Michigan Medicine Department of Urology, co-investigator on this study). Individuals with a noted and/or reported history of allergy or sensitivity to aminoglycoside antibiotics (including gentamicin) will be excluded.

*Antibiotic resistance* – It is unlikely that antibiotic resistance will be an issue in this study. The localized dosing (as opposed to systemic dosing via an oral or IV administration) used in this study will minimize the overall exposure and decrease the likelihood of altered urinary and urethral flora in response to antibiotic exposure. In fact, Cox et al actually demonstrated reduced antibiotic resistance while on gentamicin instillations.

*Confidentiality breach* – The risk of research data or PHI being accessed without study or clinical care need is very low given the standard safeguards used by Michigan Medicine as an institution and by those on the study team. Access to study-related files is granted on the basis of need by the project manager. Electronic files, including electronic consents, are protected by the Michigan Medicine information technology infrastructure, which includes digital encryption, and paper files are stored in a secure environment including locked file cabinets and restricted access offices.

*Toxicity* – The likelihood that a participant in this study would experience toxicity is quite low, as toxicity as a side effect is more associated with high doses of prolonged systemic therapy and/or in patients with impaired renal function. While high doses of gentamicin and similar compounds can be associated with nephro- and ototoxicity, these risks are minimized in this study due to the exclusion of patients with renal impairment and because the systemic absorption via the bladder has been found to be negligible. Using rats, canines and humans, Wan (1994) instilled gentamicin and evaluated serum

levels 30-minutes post-instillation. Only the rat model showed measurable, yet low, non-toxic levels of serum gentamicin; neither canine nor human tests showed any detectable concentration. In studies with limited follow-up data, there were no clinically relevant side effects. While unlikely based on these factors, gentamicin toxicity may manifest in the form of new onset and prolonged numbness, skin tingling, dizziness and vertigo. Other side effects include prolonged muscle twitching, tinnitus, roaring in the ears or hearing loss. Subjects will be instructed to remain well hydrated during study treatment, and to discontinue treatment if they experience any of these symptoms and to contact the study coordinator.

*Overdosage* – Overdosage may increase the risk of toxicity described above. The risk of this is minimal as long as subjects take study treatment as directed. As stated above, the localized dosing is unlikely to cause any increase in serum gentamicin levels and, additionally, the dose of gentamicin in each syringe is far below the threshold at which has been reported to cause adverse reactions.

*Fetal Harm* – Aminoglycosides such as gentamicin can cause fetal harm when administered to pregnant women. A pregnancy test will be administered to females of child-bearing potential at screening. Sexually active females of child-bearing age will also be asked to use appropriate contraception throughout the study while on the study treatment. Subjects who become pregnant after enrollment will be asked to discontinue the study treatment, but may remain in the study, tracking their UTIs and completing study interviews.

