### 6.5 CONCOMITANT THERAPY

For this protocol, a prescription medication is defined as a medication that can be prescribed only by a properly authorized/licensed clinician. Medications to be reported in the Case Report Form (CRF) are concomitant prescription medications, over-the-counter medications, and supplements.

During each bi-weekly call, participants will be asked about any changes in medications.. Changes will be entered into the CRF.

Concomitant use of ethacrynic acid and furosemide is not permitted in this protocol due to the increased risk of neurotoxicity. Additionally, concurrent use of systemic antibiotics for any reason is not permitted. Subjects prescribed a course of systemic antibiotic therapy will discontinue study treatment for the duration of their antibiotic course.

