## 7 STUDY INTERVENTION DISCONTINUATION AND PARTICIPANT DISCONTINUATION/WITHDRAWAL

### 7.1 DISCONTINUATION OF STUDY INTERVENTION

Participants may elect to discontinue the study intervention for any number of reasons (not inclusive list): burden of study procedures, side effects, caregiver limitations, etc. They will be educated on signs and symptoms of toxicity (see Section 8.2) and instructed to notify the study team and their physician for advice on discontinuation of study treatment. If a participant develops COVID-19 while participating in this study, the study team will make every effort to keep the participant in the trial. Participants with COVID-19 will remain in the study unless, for medical reasons, they can no longer participate.

Participants will be asked about the reasons for withdrawal from the study when self-initiated.

Regardless of the reason, discontinuation of the study treatment does not mean withdrawal from the study since the study uses an intent –to-treat design. If a participant decides to stop using the study product, and they are willing, they will remain enrolled in the study. This means that study procedures, including bi-weekly phone calls and study visits will go on as scheduled. No drug taper is required when subjects discontinue the study treatment – they may stop immediately. These subjects will also complete the study's final assessments, if willing.

Regarding the discontinuation of treatment, the following information will be documented in the study record:

- Reason for discontinuation of intervention (i.e. treatment).
- Date of last dose.
- Willingness to continue in the study.

If a participant decides to discontinue the study intervention in light of a new or exacerbated clinical finding, we will report the finding on the Adverse Event case report form, and report to the necessary entities as outlined in the Events Reporting Schedule.

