## 8.2 SAFETY AND OTHER ASSESSMENTS

- The bi-weekly phone encounters and EMR reviews are the primary means of monitoring the occurrences of side effects and participant tolerability of the Gentamicin treatment. If a participant reports a UTI or UTI symptoms, they will be advised to follow-up with their personal provider for management. Any potential manifestation of gentamicin toxicity will also be assessed during these phone encounters. These include new onset and prolonged numbness, skin tingling, dizziness, and vertigo. They also include prolonged muscle twitching, tinnitus, roaring in the ears or hearing loss. The study team will recommend subjects with these symptoms be seen by a physician for otological assessment and possible study treatment discontinuation.
- A complete blood count and comprehensive metabolic panel will be administered at baseline and six months when treatment is concluded.
- If a study-ordered urine analysis (at screening, and approximately 6-months later, defined here with a window of plus or minus 30 days) reveals an infection, participants will be instructed to follow-up with their personal provider to treat the current infection. The results of the urine test will be included in the EMR and be available to providers across institutions with EPIC access.
- During the follow-up interview (3-months post-treatment), the participant will also be asked if they have used any gentamicin instillations since being off the study drug. If they have used gentamicin, they will be asked if they are still using it. If they have not used gentamicin, they will be asked why not.

- After the follow-up interview, participants will be thanked for their participation in the trial and asked to participate in a final optional survey. If willing, they will be asked about their perceptions of the benefits and/or challenges of using Gentamicin instillations and whether they thought their participation in this trial was worthwhile. This information will be recorded in their CRFs. This option will be offered to participants at the end of their 3-months post-treatment interview and/or at a different time following this interview, depending on their availability and interest in participating.

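### For the same gentamicin toxicity symptoms, Section 2.3.1 tells participants to stop, while Sections 7.1 and 8.2 make stopping a matter for advice or assessment and do not say whether instillations are held meanwhile

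*Protocol*

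**What the plan says.** Three sections of the protocol deal with symptoms that may indicate gentamicin toxicity.

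- **Section 2.3.1, Toxicity paragraph.** After listing the symptoms, it says subjects will be instructed "to discontinue treatment if they experience any of these symptoms and to contact the study coordinator".
- **Section 7.1.** Participants are to be taught the signs of toxicity, with a pointer to Section 8.2 for what these are, and are "instructed to notify the study team and their physician for advice on discontinuation of study treatment".
- **Section 8.2.** Toxicity is assessed at the bi-weekly phone contacts, and for those affected: "The study team will recommend subjects with these symptoms be seen by a physician for otological assessment and possible study treatment discontinuation".

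The SAP does not address the matter.

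**The concern.** The participant is the first safeguard here. Instillation is nightly and at home (Section 6.1.2), the bi-weekly calls and record reviews are the main means of monitoring tolerability (Section 8.2), and dosing logs are shared only at the six-month assessment (Section 6.4). What the participant has been told to do when a symptom appears therefore matters.

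Read one after another, the sections do not give the same answer. Under 2.3.1 the participant ends dosing without needing anyone's agreement. Under 7.1 discontinuation is what the advice is about. Under 8.2 it is one possible result of a physician visit. If these are different rules for the same event, exposure after symptom onset could depend on which section a participant or coordinator works from.

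**Working it through.** No arithmetic applies: the plan states no figure on this point. The check is a comparison of text in four steps.

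**1. Do the sections cover the same events?** Yes. Section 2.3.1 lists new and prolonged numbness, skin tingling, dizziness and vertigo, then adds: "Other side effects include prolonged muscle twitching, tinnitus, roaring in the ears or hearing loss". Section 8.2 gives the same first group and continues: "They also include prolonged muscle twitching, tinnitus, roaring in the ears or hearing loss". Section 7.1 has no list of its own and refers to 8.2. The three are not separated by severity, symptom type or stage of the trial.

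**2. How do the instructions compare?**

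| | 2.3.1 | 7.1 | 8.2 |
|---|---|---|---|
| Who acts | Participant | Participant | Study team |
| Status of stopping | Automatic on any listed symptom | Subject of the advice sought | Possible, tied to a physician's assessment |
| Contact | Study coordinator | Study team and the participant's physician | Physician, on the team's recommendation |
| Dosing while waiting | Stopped; temporary or permanent not stated | Not stated | Not stated |

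Sections 7.1 and 8.2 can be read as successive steps of one process: the participant reports, and the team refers. That leaves two positions on stopping: automatic (2.3.1), or conditional on advice or assessment (7.1 with 8.2).

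**3. Do the two positions differ in practice?** Take two participants who develop tinnitus.

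- One stops that night, calls the coordinator and the physician, and is referred. All three sections are met.
- The other reports to the team and the physician the same day, but keeps instilling until seen. This breaks 2.3.1 and contravenes nothing written in 7.1 or 8.2.

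The second course is left open by silence. Neither 7.1 nor 8.2 says that instillation continues, but neither says that it is held.

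**4. Does any other text settle it?**

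- Section 5.3 has a plain rule, stop and tell the study team, but for starting a contraindicated diuretic or becoming pregnant.
- Section 6.5 uses the word for a time-limited stop: "Subjects prescribed a course of systemic antibiotic therapy will discontinue study treatment for the duration of their antibiotic course". Section 6.5.1 describes the same action as a pause followed by resumption. Both concern antibiotic courses only, where the end of the stop is defined.
- Section 7.1 adds that no taper is needed and that stopping can be immediate. That describes how to stop, not whether a symptom requires it.

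No hold rule, resumption rule or order of precedence is given for toxicity symptoms.

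**Size.** The difference in exposure is the number of instillations between symptom onset and the decision, if dosing is not held in that interval. Followed at onset, 2.3.1 implies none. For 7.1 and 8.2 the documents set no time limit on advice or assessment, so the interval has no stated length and no number can be given.

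**The case against.** The strongest reply is that the sections describe different actors at different steps (what the participant does, whom the participant tells, what the team then recommends) and fit together. On that view 2.3.1 is an immediate stop and 7.1 and 8.2 govern the later decision on permanent discontinuation; the temporary use of the same verb in 6.5 lends this some support. Part of this stands. One course of action satisfies all three sections, so a reader who inferred that staff and participants cannot all follow the protocol would be going too far. So would one who counted three incompatible rules. But the reconciling reading is written nowhere, and it does not explain why 7.1 presents discontinuation as something to seek advice about.

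It can also be said that the working instruction will sit in the training and printed information (Section 6.1.2) or the Manual of Operations (Section 10.1.8). Those are not available here and may carry a single clear rule. If so, the practical risk is smaller, but the protocol text would still disagree with itself.

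A reader might also infer from the two-week call interval that someone following 7.1 or 8.2 would keep dosing for about 14 nights. The documents do not support that. Notification under 7.1 is started by the participant and is not tied to the next call, and Section 8.1 tells participants to contact the team at any time. Delay from failing to report could occur under any of the three wordings, so it does not measure the difference between them.

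**Conclusion.** The inconsistency is real and lies in current protocol text. For one list of symptoms, 2.3.1 makes stopping automatic, while 7.1 and 8.2 make it a matter for advice or assessment. The documents do not say which governs, whether the stop in 2.3.1 is temporary or permanent, or what happens to instillations in the meantime. The first contact differs as well. Exposure after symptom onset could vary with the section followed, by an amount that cannot be derived from the documents. The number of participants affected is also unknown; 2.3.1 expects toxicity to be unlikely.

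The conclusion rests on the matching symptom lists, on 7.1's reference to 8.2, and on the absence of any reconciling rule. That dosing might continue while advice is awaited is an inference from silence.

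Two further readings are tempting and are not part of the finding.

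- *That the conflict decides who enters the primary analysis.* Section 9.3 requires use on at least half of the intervention days, but it makes no link to toxicity stops, and any effect would depend on the unknown interval and on a participant being close to that threshold.
- *That ototoxicity is the main serious drug risk.* The protocol also names nephrotoxicity, allergic reactions up to anaphylaxis and fetal harm, and ranks none of them.

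This should be corrected: it concerns a safety instruction for self-administered treatment, and the remedy is wording.

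**What to change.** Reconcile Sections 2.3.1, 7.1 and 8.2 into one instruction for suspected toxicity symptoms, stated once and cross-referenced from the other two places. It should settle:

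- whether stopping is automatic or depends on advice or assessment;
- whether instillations are held or continued while advice or assessment is pending;
- whether a stop is temporary or permanent, and who decides;
- whom the participant contacts first.

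Use the same wording in participant training, the printed instructions and the bi-weekly call script. Which rule is adopted is for the investigators and the IND sponsor to decide; this review takes no position on it.

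The cost is a wording amendment, with the IRB approval that the protocol requires for any amendment, and a matching edit to the participant materials. It adds no visits, tests or data items.
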